NCT02323646

Study ID: ZPV-201

Title: A Phase 2, Multi-Center, Parallel Design, Randomized, Double-Blind Study to Evaluate the Safety and Efficacy of 6 and 12 mg Proellex® (Telapristone Acetate) Administered Vaginally in the Treatment of Premenopausal Women with Confirmed Symptomatic Uterine Fibroids

Protocol Amendment 4 Date: 20 June 2016

*Any inconsistent numbering or deletion of pages is due to the removal of a full protocol due to its summary of changes being supplied.

ZPV201 Protocol Amendment 1 Summary of Changes

Protocol Title: A Phase 2, Multi-Center, Parallel Design, Randomized, Double-Blind Study to Evaluate the Safety and Efficacy of 6 and 12 mg Proellex® (Telapristone Acetate) Administered Vaginally in the Treatment of Premenopausal Women with Confirmed Symptomatic Uterine Fibroids

Changes From: From Original protocol, dated December 12, 2014 To: Protocol Amendment 1 dated February 24, 2015

Reason for Amendment: Change procedures, make corrections, add clarifications and change eligibility criteria

Changes to Protocol: Significant changes to the protocol are listed below.

SECTION	CHANGED FROM	CHANGED TO	REASON FOR CHANGE
LABORATORY TABLES: Table 1	
3.. Also in the event of a finding of abnormal LFT
 
7. A historical PBAC looking back over the last 28 days will be used to determine eligibility (must be >120 mL, and verified by Alkaline Hematin as $\geq 80\text{mL}$).
 
11. For subjects who had finished bleeding 5 days or less before Visit 1, Visit 2 will occur within +4 days after end of bleeding in their first menstrual event after Visit 1. For everyone else Visit 2 will occur within +4 days after end of bleeding in the second menstrual event after Visit 1.
	
3. Also as necessary to evaluate possible hepatic abnormalities
 
7. A historical PBAC looking back over the last 28 days will be used to determine eligibility (must be >120 mL, unless approved by sponsor, and verified by Alkaline Hematin as $\geq 80\text{mL}$).
 
11. A complete menstrual event must be collected before Visit 2. If subject is bleeding at Visit 1, she must wait until the last day of bleeding of this cycle, then start collecting pads the following day until the last day of bleeding in the next menstrual event. Visit 2 will occur within +4 days after end of bleeding in the first complete menstrual event after Visit 1.
	Change in procedure
[REDACTED]	[REDACTED]	[REDACTED]	[REDACTED]
PROCEDURES AND LABORATORY TABLES: Table 3		
Hypotension Questions
 
....
 
The investigator should report any of the above as adverse events.
	Clarification
[REDACTED]	[REDACTED]	[REDACTED]	[REDACTED]

SECTION	CHANGED FROM	CHANGED TO	REASON FOR CHANGE
8. TRIAL DESIGN 8.2.1 Overview of study Design	In the first stage, women will undergo a baseline assessment period, with no treatment, until 15-20 days after the start of their second or third menstrual event.	In the first stage, women will undergo a baseline assessment period, with no treatment, until 15-20 days after the start of their second complete menstrual event.	Change in procedures
8.3 Selection and Withdrawal of Subjects	
 • A need arises for concomitant medication prohibited by the protocol 	
 • A need arises for concomitant medication prohibited by the protocol, unless use of such medication is approved by the sponsor 	

SECTION	CHANGED FROM	CHANGED TO	REASON FOR CHANGE
8.3.1 Inclusion Criteria	
 Subject has a history of at least 3 regular menstrual cycles in which menorrhagia is due to uterine fibroids MBL of at least 80 mL by Alkaline Hematin Assay (during the baseline assessment period). 	
 Subject has a history of at least 3 regular menstrual cycles in which menorrhagia is due to uterine fibroids (a past or concurrent diagnosis of uterine fibroids is acceptable). MBL of at least 80 mL by Alkaline Hematin Assay (during the baseline assessment period). Subjects with evidence of prior heavy blood loss may be enrolled at the sponsor's discretion. 	Clarification
8.3.2 Exclusion Criteria	
 Use of oral contraceptives in the preceding 30 days. Use of Depo-Provera® in the preceding 10 months. Use of GnRHs (e.g. Lupron Depot) within 3 months of the first dose of study drug (Lupron Depot must have a wash-out period of 3 months) Known or suspected carcinoma of the breast or reproductive organs 	
 Use of oral contraceptives in the 30 days preceding screening. Use of Depo-Provera® in the preceding 10 months. Use of GnRHs (e.g. Lupron Depot) within 3 months prior to screening (Lupron Depot must have a wash-out period of 3 months prior to screening) History or current diagnosis of 	Change in Exclusion Criteria Clarification Clarification

SECTION	CHANGED FROM	CHANGED TO	REASON FOR CHANGE
	[REDACTED]	malignancy other than curatively treated basal cell carcinoma	[REDACTED]
	[REDACTED]	[REDACTED]	[REDACTED]
	[REDACTED]	[REDACTED]	[REDACTED]

SECTION	CHANGED FROM	CHANGED TO	REASON FOR CHANGE
	[REDACTED]	[REDACTED]	[REDACTED]
	[REDACTED]	[REDACTED]	[REDACTED]
	[REDACTED]	[REDACTED]	[REDACTED]

~~their next cycle (first cycle after Visit 1).~~

SECTION	CHANGED FROM	CHANGED TO	REASON FOR CHANGE
	[REDACTED]	[REDACTED]	

SECTION	CHANGED FROM	CHANGED TO	REASON FOR CHANGE
12. Statistical Methods 12.2 Statistical and Analytical Plan		
A Statistical Analysis Plan (SAP) will be prepared prior to unblinding the data. The first efficacy analysis will be conducted when all subjects complete the first cycle of treatment. A second analysis will summarize the subject's additional treatment cycles which will be conducted after all subjects complete study treatment and follow-up in Stage 2. In this Phase 2 study there will be no statistical corrections for interim analyses or multiple comparisons.
 
For the statistical analysis at the end of the first course of treatment, only statistical staff will be unblinded. All clinical operations staff and staff at investigative sites will remain blinded until completion of the study.
	Clarification

SECTION	CHANGED FROM	CHANGED TO	REASON FOR CHANGE
[REDACTED]	[REDACTED]	[REDACTED]	
[REDACTED]	[REDACTED]	[REDACTED]	[REDACTED]

SECTION	CHANGED FROM	CHANGED TO	REASON FOR CHANGE
	[REDACTED]	[REDACTED]	
	[REDACTED]	[REDACTED]	

ZPV-201 Amendment 2 Protocol Summary of Changes

Protocol Title: A Phase 2, Multi-Center, Parallel Design, Randomized, Double-Blind Study to Evaluate the Safety and Efficacy of 6 and 12 mg Proellex® (Telapristone Acetate) Administered Vaginally in the Treatment of Premenopausal Women with Confirmed Symptomatic Uterine Fibroids

Changes From: From Protocol Amendment 1 dated February 24, 2015 To: Protocol Amendment 2 dated September 4, 2015

Reason for Amendment: Changes study requirements for endometrial stripe $\geq 18\text{mm}$.

Changes to Protocol: Significant changes to the protocol are listed below.

SECTION	CHANGED FROM	CHANGED TO	REASON FOR CHANGE
8.3 Selection and Withdrawal of Subjects	
 • [REDACTED] 	
 • [REDACTED] 	
 • Any subject who experiences heavy bleeding (bleeding intensity of 4 or more per the Daily Diary Card in Appendix 4) for 7 consecutive days or more will be discontinued from the study. This does not

SECTION	CHANGED FROM	CHANGED TO	REASON FOR CHANGE
		apply if heavy bleeding occurs in the first recovery menses after withdrawal of drug at the end of Course 1 or Course 2, or is no heavier than bleeding was prior to treatment.	
[REDACTED]		[REDACTED]	[REDACTED]
[REDACTED]	[REDACTED]		

ZPV-201 Amendment 3 Protocol Summary of Changes

Protocol Title: A Phase 2, Multi-Center, Parallel Design, Randomized, Double-Blind Study to Evaluate the Safety and Efficacy of 6 and 12 mg Proellex® (Telapristone Acetate) Administered Vaginally in the Treatment of Premenopausal Women with Confirmed Symptomatic Uterine Fibroids

Changes From: From Protocol Amendment 2 dated September 4, 2015 To: Protocol Amendment 3 dated April 8, 2016

Reason for Amendment: Addition of Alkaline Hematin Assay at the end of Course 2

Changes to Protocol: Significant changes to the protocol are listed below.

SECTION	CHANGED FROM	CHANGED TO	REASON FOR CHANGE
Protocol Synopsis-Study Design and Duration of Treatment	Subjects will collect and return used sanitary materials for alkaline hematin assay for their first menstrual event during screening, for the recovery menses following Courses 1 and 2 and for the 2 nd , 4 th and 6 th menstrual cycles after end of treatment in Course 2.	Subjects will collect and return used sanitary materials for alkaline hematin assay for their first menstrual event during screening, for the recovery menses following Course 1, for the 28 days leading up to the end of treatment in Course 2, and for the 1st, 2nd, 4th and 6th menstrual cycles after end of treatment in Course 2.	Addition of Alkaline Hematin assay at the end of Course 2
8.2.1 Overview of Study Design		
Statement added:
 
Sanitary products will be collected for alkaline hematin assay during the following timepoints:
 
 From the 28 days leading up to end of treatment in Course 2 (Visit 18) 	Addition of Alkaline Hematin assay at the end of Course 2
8.2.6 Endometrial Biopsies		
Statement added:
 

	Clarification

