	up to the end of treatment in Course 2, and for the 1 st , 2 nd , 4 th and 6 th menstrual cycles after end of treatment in Course 2.
Subject Population:	The study will enroll healthy adult, pre-menopausal women with confirmed uterine fibroids via MRI and confirmed menorrhagia (>120 mL blood loss per menstrual cycle by historical PBAC assessment, nominal 28 days to ensure a MBL of at least 80 mL by Alkaline Hematin Assay). Subjects with evidence of prior heavy blood loss may be enrolled at the sponsor's discretion.
Number of Subjects:	Up to 45 female subjects, 15 per dose arm
Number of Sites	Approximately 10 sites
Study Duration:	Total participation in the study is approximately 18 months.
Study Endpoints	
The primary endpoint will be:
 
• Percentage of subjects who become amenorrheic after one course of treatment 
Secondary endpoints will be:
 
• Percentage of subjects who become amenorrheic after 2 courses of treatment

	
• Change and percentage change in PBAC score over the course of the study. Specifically comparing the baseline menstrual cycle to the matching end-of-study period leading up to Week 18 and the end of treatment as well as comparing the baseline PBAC to the ODI time periods.• Percentage change in UFSQOL Symptom Severity score (UFS-SSS) comparing Week 18 to Baseline (three month look back) and for the ODI.• Percentage change in the individual UFS-SSS sub scores• Percentage change from baseline in total uterine fibroid volume measured by MRI                   
Statistical Methods:	A Statistical Analysis Plan (SAP) will be developed prior to unblinding of the data that will outline all planned analyses and analysis populations. The first efficacy analysis will be conducted when all subjects complete the first cycle of treatment. A second analysis will summarize the subject's additional treatment cycles which will be conducted after all subjects complete study treatment

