8.2 Study Design

8.2.1 Overview of Study Design

This study is a phase 2 3-arm-study with a 36 week active dosing period. The study will be conducted in two stages.

[figure not shown]
[figure not shown]
[figure not shown]
In the first stage, women will undergo a baseline assessment period, with no treatment, until 15-20 days after the start of their second complete menstrual event. During this phase a pictorial blood loss assessment chart and daily diaries will be utilized. Used sanitary products from the first menstrual event will be collected and returned to the clinic for alkaline hematin assay. This assay will confirm subject eligibility (MBL must be 80 mL or greater by alkaline hematin assay for subjects to qualify).

In the second stage, subjects will be randomized into one of 3 arms in a 1-1-1 fashion. The start of the 18 week dosing period (Course 1) in this stage of the study should commence 15-20 days after the start of their first menses after Visit 2. Once active dosing is stopped, subjects will be followed until menses returns. The start of the second 18 week dosing period (Course 2) will commence 15-20 days after the start of their menses following withdrawal of drug after Course 1 has been completed. During the non dosing off-drug interval (ODI), subjects will continue to record study information in the daily paper diary and PBAC charts.

After end of dosing in Course 2, subjects will be followed through the subsequent recovery menses and for an additional 5 menstrual events, after which the subject may be offered the opportunity to enroll in an extension study. Subjects who fail to achieve amenorrhea may enroll in the extension study at Visit 19. Amenorrhea is defined as any 28-day period during treatment (not including the ODIs) without a bleeding score >1. Throughout the study women will record study information in the diary, PBAC and questionnaires as outlined in the study procedures.

In addition to the diary information, endometrial thickness will be recorded at screening and every month thereafter. Assessment of

trough levels of drug will be determined at every office visit during the first and second 18 week dosing periods.

The primary efficacy analysis will be conducted when all subjects complete the first cycle of treatment. A second analysis will summarize the subject's second treatment cycle which will be conducted after all subjects complete study treatment and follow-up.

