8.2.3 Randomization and Blinding

At Visit 3, subjects will be randomized to treatment in Arms 1, 2, or 3. Subjects will be treated with one capsule daily of 6 mg or 12 mg of Proellex, or placebo, which will be administered for a total of 36 weeks (two 18 week courses separated by an ODI) before the 6 cycle follow up is started. After the second treatment course is completed the subjects will be followed for 6 menstrual events to determine durability of effect of treatment, after which they may be offered the opportunity to enroll in an open-label extension study. Subjects who fail to achieve amenorrhea may enroll in the extension study at Visit 19. Amenorrhea is defined as any 28-day period during treatment (not including the ODIs) without a bleeding score >1. Each treatment course will be separated by an ODI. Blinded treatments kits will be randomized and distributed by the packaging company.

For the statistical analysis at the end of the first course of treatment, only statistical staff will be unblinded. All clinical operations staff and staff at investigative sites will remain blinded until completion of the study.

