14. INVESTIGATOR'S STATEMENT

[figure not shown]
I have reviewed the ZPV-201 protocol and Investigator Brochure and agree to conduct this study as outlined in the protocol and in compliance with ICH/GCP Guidelines.

[figure not shown]
Investigator

[figure not shown]
Date

[figure not shown]
Printed name

[figure not shown]

[figure not shown]

[figure not shown]

[figure not shown]

[figure not shown]

[figure not shown]

ZPV-201 Amendment 4 Protocol Summary of Changes

Protocol Title: A Phase 2, Multi-Center, Parallel Design, Randomized, Double-Blind Study to Evaluate the Safety and Efficacy of 6 and 12 mg Proellex® (Telapristone Acetate) Administered Vaginally in the Treatment of Premenopausal Women with Confirmed Symptomatic Uterine Fibroids

Changes From: From Protocol Amendment 3 dated April 8, 2016 To: Protocol Amendment 4 dated June 20, 2016

Reason for Amendment: Addition of MRI at Visit 24, addition of requirements for enrollment in Extension Study

Changes to Protocol: Significant changes to the protocol are listed below.

SECTION	CHANGED FROM	CHANGED TO	REASON FOR CHANGE
Protocol Synopsis-Study Design and Duration of Treatment	After completion of stage 2 dosing (Courses 1 and 2), subjects will be followed through the subsequent 6 menses (recovery menses plus an additional 5 menstrual events). In the event that a subject's menstrual bleeding returns to $\geq 80\text{mL}$ (assessed by alkaline hematin assay) at the end of this period, the subject may be offered the opportunity to enroll in an extension study.	After completion of stage 2 dosing (Courses 1 and 2), subjects will be followed through the subsequent 6 menses (recovery menses plus an additional 5 menstrual events), after which (at Visit 24) the subject may be offered the opportunity to enroll in an open-label extension study. Subjects who fail to achieve amenorrhea may enroll in the extension study at Visit 19. Amenorrhea is defined as any 28-day period during treatment (not including the ODIs) without a bleeding score >1 .	Change in study design

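### Carry-forward of missing efficacy data is not confined to time on drug, so off-drug durability values (later menses, Visit 24 MRI) could be filled with end-of-treatment values

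*Protocol*

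**What the plan says.** **Purpose of the follow-up.** Protocol 8.2.3 states that after Course 2 "the subjects will be followed for 6 menstrual events to determine durability of effect of treatment". The synopsis counts these as the recovery menses plus five more, and collects pads for alkaline hematin at the 1st, 2nd, 4th and 6th "menstrual cycles after end of treatment in Course 2". Protocol 12.2.2.2 uses PBAC to find the time to return to baseline bleeding, and measures fibroid volume by MRI at the end of each course and at Visit 24.

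**Missing data.** Protocol 12.2.2.2 applies carry-forward to PBAC, for which summaries are planned at visits beyond Week 18, and to fibroid volume, for which analyses continue at every volume assessment. Protocol 12.3 applies carry-forward to efficacy variables generally. SAP 6.1 also uses carry-forward, defined as the last value recorded on treatment.

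**Withdrawal for bleeding.** The Amendment 2 summary gives wording for 8.3: a woman with diary intensity of 4 or more "for 7 consecutive days or more will be discontinued from the study". By timing, the rule does not "apply if heavy bleeding occurs in the first recovery menses after withdrawal of drug at the end of Course 1 or Course 2". A second exemption concerns severity, and takes out a bleed that meets this condition: "or is no heavier than bleeding was prior to treatment". The current text of 8.3 is redacted. The stated reasons for the next two amendments are "Addition of Alkaline Hematin Assay at the end of Course 2" and "Addition of MRI at Visit 24, addition of requirements for enrollment in Extension Study".

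**Other exits.** Protocol 8.2.1 adds: "Subjects who fail to achieve amenorrhea may enroll in the extension study at Visit 19".

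**The concern.** The six off-drug menses and the Visit 24 MRI exist to show whether benefit lasts once the drug is gone. A value recorded on drug carries no information about that. If it is entered for a missing off-drug time point, the summary shows continued control or no regrowth where nothing was observed.

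The harm is greater when values are missing because the outcome was bad, and the Amendment 2 rule would produce that kind of gap. After the last Course 2 dose there is no drug left to stop, yet the wording ends study participation rather than dosing. Follow-up is already selected to some degree, because women who do not reach amenorrhea may move to the extension at Visit 19. The withdrawal rule would add selection among those who stay.

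**Working it through.** **1. Time points the fill reaches**

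| Source | Scope of carry-forward | Off-drug time points excluded? |
|---|---|---|
| Protocol 12.2.2.2, PBAC | Week 18 is primary; other visits also summarised | No |
| Protocol 12.2.2.2, MRI | Every volume assessment, including Visit 24 | No |
| Protocol 12.3 | Efficacy variables generally | No |
| SAP 6.1 | Efficacy variables, last on-treatment value | No |

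The SAP 6.8.2 list of PBAC intervals is not visible, so the intended scope cannot be read from it.

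**2. Value that is copied**

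- *MRI.* After baseline, volumes come at the end of Course 1, the end of Course 2 and Visit 24. The last observation before Visit 24 is also the last on treatment, so both rules insert the end-of-Course-2 volume.
- *Bleeding.* The rules diverge. SAP 6.1 inserts an on-drug value. Protocol 12.3 inserts the most recent observed menses, which for a woman removed by the 8.3 rule is the triggering bleed. The two push the mean in opposite directions.

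**3. Size for MRI**

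With *n* = 15 per arm (protocol 12.1), *k* women filled with zero regrowth, and their true regrowth equal to the arm mean *g*, the reported mean is (*n* − *k*)*g*/*n*. The understatement is *k*/*n*: 1/15 = 6.7%, 2/15 = 13.3%, 3/15 = 20.0%.

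**4. What one trigger would cost, if the Amendment 2 wording applies**

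There are 6 menses and only the first is exempt by timing. A trigger in menses *j* loses 6 − *j* later menses.

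| Trigger in menses | Later menses lost | Hematin collections lost (of menses 1, 2, 4, 6) |
|---|---|---|
| 2 | 4 | 4 and 6 |
| 3 | 3 | 4 and 6 |
| 4 | 2 | 6 |
| 5 | 1 | 6 |

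The Visit 24 MRI is lost in each case unless it is done at exit. A trigger in menses 6 loses no later menses.

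**5. Illustrative size for bleeding**

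The documents give no trigger rate, SD or correlation, so every input in this step is an assumption. Bleeding relative to baseline in menses 2 to 6 is lognormal with median *m* = 0.8, log SD *s* = 0.6 and log-scale correlation *r* = 0.5. A woman is removed at the first of menses 2 to 5 in which her ratio exceeds 1 and, with probability *q*, the 7-day criterion is also met. The table gives the shift in the menses 6 mean against complete data (1,000,000 simulated women per scenario).

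| *q* | Removed of 15 | As observed | On-treatment fill = 0 | On-treatment fill = 0.2 of baseline | Trigger carried forward |
|---|---|---|---|---|---|
| 2% | 0.42 | −0.9% | −3.7% | −3.1% | +0.9% |
| 5% | 1.02 | −2.4% | −9.0% | −7.6% | +2.2% |
| 10% | 1.96 | −4.7% | −17.1% | −14.4% | +4.4% |

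Hand check at 5%: the fraction removed is 1.02/15 = 0.068. A zero fill leaves 1 − 0.090 of the mean, so the as-observed mean is (1 − 0.090)/(1 − 0.068) = 0.976, or −2.4%, as simulated.

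Sensitivity at *q* = 5%:
- *m* = 0.6 removes 0.58 women (as observed −1.9%, zero fill −5.7%).
- *m* = 1.0 removes 1.43 women (−2.4%, −11.7%).
- Varying *r* from 0.3 to 0.7, or *s* from 0.4 to 0.8, keeps the as-observed shift between −1.4% and −3.3%.

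If the trigger is instead a ratio above 2, 2.5 or 3, removals are 2.7, 1.3 and 0.7 of 15. The shifts are then −12.5/−7.5/−4.4% as observed, −28.0/−15.7/−8.8% with a zero fill, and +20.1/+13.6/+8.9% with the trigger carried forward.

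**6. Yardstick**

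The relative standard error of a 15-woman mean is √(exp(0.36) − 1)/√15 = 17.0%. Summarising as observed stays below this in every scenario. A fill can reach or exceed it.

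**The case against.** **The withdrawal rule may not operate this way.** It is visible only in the Amendment 2 summary. Current 8.3 is redacted, and the visit procedures, where exit assessments would normally appear, are not visible. A reader might infer from the stated reasons for Amendments 3 and 4 that the rule is unchanged. The documents do not support that: Amendment 2's own stated reason concerns only the endometrial stripe, yet its table contains this rule, so stated reasons do not list every change. Some rows of the later summaries are also redacted. This objection stands, and the 8.3 part is therefore conditional. What can be said is that the wording, if in force, reaches off-drug follow-up, because a rule confined to dosing would not need an exemption for the recovery menses after Course 2.

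**Ordinary relapse does not trigger removal.** A reader might infer that any return of heavy menses ends participation. The second exemption rules that out, since bleeding must exceed the pre-treatment level. A woman removed by the rule has therefore already shown loss of benefit, and her time to return to baseline is observed. This stands too.

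**SAP 6.1 may be meant for on-treatment time points only.** That is a fair reading of the intent. The text does not say so, and protocol 12.2.2.2 extends carry-forward to volume assessments that include Visit 24. If it is the intent, one sentence settles the matter.

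**The rates are assumed and the threshold may be a deliberate safety choice.** Both are true. The trigger needs a week of intensity 4 or more and bleeding above baseline, in women who already bled heavily, so it could be close to never met. The fix leaves the threshold alone.

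**Conclusion.** The firm part rests on visible text. Carry-forward is not limited to time on drug, so a missing Visit 24 MRI would be recorded as no regrowth and, under SAP 6.1, a missing off-drug menses would receive an on-drug value. Each MRI filled in this way understates an arm's mean regrowth by about 6.7%, assuming 15 women per arm and average regrowth in the woman filled.

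The 8.3 rule is a possible contributor. It depends on the Amendment 2 wording still applying and on no redacted text providing exit or continued assessments. Dropping the affected women is minor in the main scenarios (−0.9 to −4.7% against a 17% standard error). The fill is the larger problem.

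A reader might infer that the main efficacy result is at risk or that the bias favours Proellex over placebo. Neither follows. The primary endpoint and the Week 18/Visit 12 assessments of PBAC, UFS-SSS and MRI lie outside this off-drug period. The number affected and the direction between arms are unknown, and the protocol and SAP fills move the bleeding mean in opposite directions. This is a low-priority recommendation, bordering on optional.

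**What to change.** **SAP 6.1.** Limit the last on-treatment value to on-treatment time points. Summarise off-drug menses and Visit 24 as observed, with the number of women observed per arm at each. State that this replaces the carry-forward sentences of protocol 12.2.2.2 and 12.3 for those time points.

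**Protocol 8.3.** Keep the bleeding threshold. After the last Course 2 dose, have it trigger clinical evaluation instead of removal from the study. Assessments already scheduled (diary, PBAC, hematin, MRI) would continue to Visit 24 for women who agree. UFS-SSS should follow whichever schedule is confirmed, because protocol 12.2.2.2 places it at the start and end of each course while SAP 6.8.3 also refers to follow-up visits. Flag values recorded after any rescue treatment, since protocol 11.1 prohibits hormonal and other fibroid treatment during follow-up.

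**Cost.** These are wording changes with no new visit or procedure. Recovery of data will be partial: some women will decline to continue, and others will have later values flagged and of limited use for durability.
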